### **6.3.5.2. Analysis**

Summary statistics of actual values and changes from baseline to each scheduled visit in ACQ-6 score will be provided by previous double-blind treatment group and for all patients. A line graph presenting the mean change from baseline over time (at each visit) will be provided for the overall score by previous double-blind treatment group.

## **6.3.6. Asthma Quality of Life Questionnaire for Patients 12 Years and Older**

### **6.3.6.1. Definition**

The AQLQ +12 is a modified version of the standardized AQLQ (AQLQ[S]), which was developed to measure functional impairments experienced by adults  $\geq 17$  years of age. The AQLQ +12 is valid for patients 12 to 70 years of age and includes 32 questions in 4 domains (symptoms, activity limitation, emotional function, and environmental stimuli). Patients will be asked to recall their experiences during the previous 2 weeks and score each of the questions on a 7-point scale, where 7=not at all limited and 1=totally limited

The 32 questions (items) in the AQLQ +12 are divided into 4 domains:

- Activity limitations: Items 1-5, 11, 19, 25, 28, 31, 32
- Symptoms: Items 6, 8, 10, 12, 14, 16, 18, 20, 22, 24, 29, 30
- Emotional function: Items 7, 13, 15, 21, 27
- Environmental stimuli: Items 9, 17, 23, 26

[figure not shown]
### **6.3.6.1.1. Missing data handling and total score calculation**

The overall and domain scores of the AQLQ +12 are derived as the average of the corresponding items; the analysis will be based on the available data.

For incomplete data, the overall AQLQ +12 score for a particular visit will not be calculated if 3 or more responses are missing with no more than 1 per domain. For the symptom and activity domain total scores, calculation will require no more than 1 missing item. Total scores for the other 2 domains will be regarded as missing if 1 or more item is missing.

### **6.3.6.2. Analysis**

Summary statistics of actual values and change from baseline to each scheduled visit in the overall and domain scores of AQLQ + 12 will be provided by previous double-blind treatment group and for all patients. A line graph presenting the mean change from baseline over time (at each visit) will be provided for the overall score by previous double-blind treatment group.

## **7. MULTIPLE COMPARISONS AND MULTIPLICITY**

There are no pre-specified adjustments for multiplicity applied to this study.

## 8. SAFETY ANALYSIS

### 8.1. General

The safety analysis set (Section 3.2) will be used for all safety analyses unless otherwise noted. Summaries will be presented by double-blind treatment group in the previous studies 30025 and 30027 (placebo and reslizumab) and for all patients (ie, total), unless otherwise noted.

For continuous variables, descriptive statistics (n, mean, SD, SE, median, minimum, and maximum) will be provided. For categorical variables, patient counts and percentages will be provided. Categories for missing data will be presented if necessary.

### 8.2. Study Drug Administration

The exposure to study drug will be characterized by duration of treatment and by the number of patients receiving at least 1, 2, 3, etc. injections. Total patient years will also be summarized. The summaries will be provided by previous double-blind treatment group and for all patients.

Duration of treatment period is defined separately for patients who completed/discontinued treatment.

- Completed: End of treatment (week 36) visit date – first dose date + 1
- Discontinued: Last dose date – first dose date + 29

For non-seamless rollovers, the length of the “gap” between the end of study drug administration from the previous double-blind study to the start of study drug administration in this study will also be summarized.

### 8.3. Adverse Events

Adverse events will be coded using the Medical Dictionary for Regulatory Activities (MedDRA); the final version number will be indicated in the summary tables.

On-treatment adverse event summaries will be presented by previous double-blind treatment group and for all patients, based on events with onset during the treatment period. If the AE start date is missing or partial, the event will be considered on-treatment unless there is evidence to the contrary (eg, month and year of AE start is present and is less than the month and year of the first dose of study drug). Post-treatment adverse events with onset during the follow-up period (ie, AE start date greater than the upper bound of the treatment period, as described in Section 4.4 previously) will be summarized separately.

Summaries will be presented by SOC and/or PT for all adverse events (overall and by severity), adverse events determined by the investigator to be related to study treatment (overall and by severity), serious adverse events, adverse events causing discontinuation from study treatment, and non-serious adverse events. Treatment related adverse event summaries will include events with missing relationship to study drug. For summaries by severity, patients will be counted at the greatest reported severity. Adverse events missing the flag indicating a serious adverse event will be excluded from the summary of serious adverse events, but included in the summary of non-serious adverse events.

In addition, adverse events that begin within 24 hours after study drug injection and injection-site adverse events (as recorded on the CRF) will each be summarized separately.

A summary for the most common adverse events (incidence  $\geq 2\%$  for all patients) will also be presented. Adverse events will additionally be presented for subgroups defined in Section 3.3.

All adverse events, including events with onset prior to the first dose of reslizumab in this study, will be included in the patient listings. The mapping of MedDRA dictionary terms for adverse event descriptions will also be provided.

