9.6. Safety Analysis

Safety analyses will be performed on the safety analysis set (see Section 9.2.2).

Safety assessments and time points are provided in Table 1. For all clinic-based safety variables measured and summarized over time, baseline will be defined as the last observation recorded before administration of the first dose of reslizumab in the OL extension study.

All adverse events will be coded using the Medical Dictionary for Regulatory Activities (MedDRA). Each patient will be counted only once in each preferred term or system organ class category for the analyses of safety. Summaries will be presented for all adverse events (overall and by severity), adverse events determined by the investigator to be related to test IMP (ie, reasonable possibility; see Section 7.1.4) (defined as related or with missing relationship) (overall and by severity), serious adverse events, and adverse events causing withdrawal from

the study. Summaries will be presented for all patients. Patient listings of serious adverse events and adverse events leading to withdrawal will be presented.

For continuous variables of safety measures, descriptive statistics (n, mean, SD, median, minimum, and maximum) will be provided for actual values and changes from baseline to each time point. For categorical variables, patient counts and percentages will be provided.

Descriptive summaries of serious adverse events, patient withdrawals due to adverse events, and potentially clinically significant abnormal values (clinical laboratory or vital signs) based on predefined criteria will be provided.

The use of concomitant medications will be summarized by therapeutic class using descriptive statistics. Concomitant medications will include all medications taken while the patient is treated with reslizumab.

If any patient dies during the study, a listing of deaths will be provided, and all relevant information will be discussed in the patient narrative included in the CSR.

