## 1. STUDY OBJECTIVES AND ENDPOINTS

### 1.1. Primary and Secondary Study Objectives and Endpoints

The primary objective of this study is to support the long-term safety of reslizumab 110 mg administered subcutaneous (sc) once every 4 weeks in patients 12 years of age and older with severe eosinophilic asthma that is inadequately controlled on standard-of-care treatment.

The primary endpoint is frequency of all adverse events including serious adverse events.

The secondary safety endpoints for this study include the following:

- clinical laboratory test results – hematology and chemistry results at baseline and at weeks 4 (chemistry only), 8, 24, and 36 or early withdrawal visit
- local tolerability at the injection site at approximately 1 hour after study drug administration every 4 weeks throughout the study
- vital signs measurements every 4 weeks throughout the study
- concomitant medication usage every 4 weeks throughout the study

The secondary objective of this study is to evaluate the efficacy of reslizumab 110 mg administered sc once every 4 weeks in patients 12 years of age and older with severe eosinophilic asthma that is inadequately controlled on standard-of-care treatment.

The secondary efficacy endpoints for this study include the following:

- clinical asthma exacerbation (CAE) and healthcare utilization (HCU)-related endpoints
  - frequency of CAEs
  - frequency of asthma-specific hospital admissions
  - length of hospital stay and number of Intensive Care Unit (ICU) days
  - frequency of asthma-specific emergency department visits
  - frequency of school/work days missed due to asthma
- change from baseline in pre-bronchodilator Forced Expiratory Volume in 1 Second (FEV1) measured using spirometry at weeks 0, 8, 24, and 36 or early withdrawal visit
- change in daily morning ambulatory FEV1 from baseline at each week through week 36 or early withdrawal, as measured by the handheld spirometry device.
- absolute and percent reduction in the daily Oral Corticosteroid (OCS) dose at weeks 20 and 36 or early withdrawal visit as compared with the dose at baseline (for patients on daily OCS at baseline).
- change from baseline in total inhalations of reliever bronchodilator medication (eg, short-acting beta agonist) measured using weekly averages until week 36 or early withdrawal visit.

- change from baseline in Asthma Control Questionnaire (ACQ-6) score performed at weeks 0, 8, 24, and 36 or early withdrawal visit

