## **2.4. Sample Size and Power Considerations**

The sample size for this study is not based on power considerations. The sample size is determined by the number of patients anticipated to rollover from the 2 double-blind, placebo-controlled, Phase 3 studies of reslizumab sc (Studies 30025 and 30027).

Approximately 360 patients will be enrolled in this study. The objective of this study is primarily safety oriented; therefore, no formal hypothesis testing is planned. Patients completing at least the full treatment periods of Studies 30025 and 30027 (or through at least the early follow-up visit for adolescents from Study 30025) and meeting the protocol's inclusion criteria and none of the exclusion criteria are eligible for enrollment in this study. It is estimated that the majority of patients enrolled in eligible reslizumab safety and efficacy studies will rollover to this study.

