## **2.5. Sequence of Planned Analyses**

### **2.5.1. Planned Interim Analyses**

There will be a planned data cut will be produced before the supplemental Biologics License Application (sBLA) submission. For the purpose of this analysis, a data cut-off will be established in accordance with the targeted date of submission and an interim CSR will be prepared. All outputs identified in this SAP and planned for the final analysis (Section 2.5.2) will be prepared at this time. The interim CSR to support sBLA submission will be based on all data accumulated from the study start to December 2017.

An additional planned data cut will be produced before the Day 120 safety update report, following the sBLA submission. For the purpose of this analysis, a data cut-off will be established in accordance with the targeted date of submission and safety data from this study

will be integrated with safety data from the other studies within the Day 120 report (in this case, there will be no separate interim CSR). The summaries provided at the time of this data cut will be consistent with those planned for the Summary of Clinical Safety (SCS) in the sBLA.

At the time of each planned interim analysis, no individual patient's data are considered fully locked; therefore interim results are interpreted as preliminary.

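### Adverse events with a blank seriousness flag are counted as non-serious, so the SAE summary can only be right or too low

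*SAP*

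**What the plan says.** SAP Section 8.3 sets three rules for adverse event records with a missing attribute.

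- **Seriousness:** "Adverse events missing the flag indicating a serious adverse event will be excluded from the summary of serious adverse events". The sentence goes on to place them in the non-serious table instead. The rule has no exception.
- **Relationship:** "Treatment related adverse event summaries will include events with missing relationship to study drug". Protocol Section 9.6 agrees, describing related events as "defined as related or with missing relationship".
- **Start date:** "If the AE start date is missing or partial, the event will be considered on-treatment unless there is evidence to the contrary".

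The protocol has no rule for a missing seriousness flag. SAP Section 14 (Table 7) lists only the added data cut as a change from the protocol.

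SAP Section 1.1 names SAEs in the primary endpoint: "The primary endpoint is frequency of all adverse events including serious adverse events".

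SAP Section 2.5.1 plans an interim clinical study report for the sBLA, containing every output planned for the final analysis. It says that at each interim analysis no individual patient's "data are considered fully locked", and that interim results are therefore preliminary.

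**The concern.** A blank flag means that seriousness is unknown in the database. The SAP turns that unknown into non-serious in two tables at once: the event leaves the SAE summary and enters the non-serious one. The other two rules in the section lean towards attributing more to treatment, and the start-date rule gives way to contrary evidence. The seriousness rule leans the other way and gives way to nothing. Read literally, an event that led to a hospital admission but has a blank flag would be tabulated as non-serious even if the sponsor already held its SAE form. No reason for the difference is given.

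At stake is the SAE table of a long-term safety study, above all in the interim report that supports a regulatory submission, when data queries may still be open.

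**Working it through.** There is no stated figure to reproduce: the study is descriptive, and the documents give no rate of missing flags. The check is one of direction, then of illustrative size.

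**Direction.** Take the three rules side by side.

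| Missing attribute | Resolved towards | Yields to contrary evidence? |
|---|---|---|
| Relationship | related | not stated |
| Start date | on-treatment | yes |
| Seriousness | non-serious | no |

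Let S be the number of patients who truly have an SAE, and m the number of those whose only SAE records have a blank flag. Assume that flags which are filled in are correct. The SAP rule reports S − m. Since m ≥ 0, the reported count equals S or falls below it, and it cannot exceed S. By the same reasoning, the non-serious count is either correct or too high. The count of patients with any adverse event does not use the flag and is unchanged.

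**Size, for illustration.** Inputs:

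- N = 360, from SAP Section 2.4: "Approximately 360 patients will be enrolled in this study". This is planned enrolment, used here in place of the safety analysis set.
- SAE incidence of 6%, the figure for intravenous reslizumab 3.0 mg/kg in Protocol Section 1.2.2.2.2. Applying it to this subcutaneous study is an assumption.
- m from 1 to 5, an assumed range.

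Expected SAE patients: 0.06 × 360 = 21.6, taken as S = 22, so the true incidence is 22/360 = 6.1%. Each affected patient shifts incidence by 1/360 = 0.28 percentage points.

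| m | Reported under SAP rule, (22 − m)/360 | Relative understatement, m/22 |
|---|---|---|
| 1 | 21/360 = 5.8% | 4.5% |
| 2 | 20/360 = 5.6% | 9.1% |
| 3 | 19/360 = 5.3% | 13.6% |
| 5 | 17/360 = 4.7% | 22.7% |

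**The opposite error.** Suppose unresolved blanks are counted as serious, all of them are in truth non-serious, and each belongs to a patient with no other SAE. The count is then (22 + m)/360: 23/360 = 6.4% for m = 1, and 27/360 = 7.5% for m = 5. The shift per patient is the same, in the other direction. This is why reconciliation should come before any default.

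The per-patient shift is 100/n percentage points, so it is larger where n is smaller: at the interim cut if fewer patients have been treated, and within each previous double-blind treatment group (SAP Section 8.1). The documents do not give those numbers.

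**The case against.** The case for leaving the rule alone has several parts.

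**Few flags should be blank.** Protocol Section 7.1.2 requires the investigator to record seriousness for every event. Section 7.1.5.3.1 requires SAEs to reach the sponsor on a separate form within 24 hours. Appendix T sends missing data back to the centre as queries. This stands and limits the size at final lock. It does not defend the rule: if blanks are rare, a better default costs almost nothing.

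**Non-serious is the protocol's residual category.** Protocol Section 7.1.5.1 treats an event meeting no seriousness criterion as non-serious. But that describes an event that has been assessed, and a blank flag records no assessment.

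**Worst-case handling is not uniform in the SAP.** Section 8.3 gives no such rule for missing severity, and Section 4.3 does not impute in general. This is true. The contrast holds only for relationship and start date.

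**A blank event may well be non-serious.** This stands as an argument against pure worst-case counting, and it shapes the fix.

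**A category for missing data is already allowed.** SAP Section 8.1 permits one if necessary, but the specific sentence in Section 8.3 sends these events to the non-serious table.

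A reader might also infer two stronger points that the documents do not support. One is that the primary result is biased. The protocol synopsis defines that analysis as the count and percentage of patients with at least one adverse event, which the flag cannot change; only the SAE component is touched. The other is that the rule governs both regulatory data cuts. SAP Section 2.5.1 ties the SAP outputs to the sBLA interim report. For the Day 120 update it describes integrated summaries consistent with the Summary of Clinical Safety and no separate interim report, so it is not shown that Section 8.3 applies there.

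**Conclusion.** The point holds as a minor one. The rule can leave the SAE summary only correct or too low, provided flags that are filled in are correct, and it is out of line with the handling of missing relationship and start date in the same section. The loss is 0.28 percentage points per affected patient at N = 360. The number affected is unknown and probably small at final lock. The main exposure is the sBLA interim report; that blanks are commoner before lock is a reasonable inference, not a documented fact. Affected events remain in the all-event summary and the patient listings, and deaths are listed separately (SAP Section 8.4), so the information is misclassified rather than lost. Nothing in the documents shows that SAEs will in practice be materially understated.

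**What to change.** Amend the sentence in SAP Section 8.3 as follows.

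1. Before the sBLA interim cut and again at final lock, reconcile every adverse event with a blank seriousness flag against the SAE forms already received.
2. Include any event still unresolved in the SAE summary, with the number of such events footnoted. At minimum, show them in a separate row for missing seriousness.
3. Do not count them as non-serious.

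This is a cheap improvement: a short text change and a reconciliation step, with no new data collection. The downside is a possible slight over-count of SAEs and a slightly less favourable figure. The footnote lets the reader see how much of the count depends on the default.

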### **8.3.1. Adverse Events of Special Interest**

#### **8.3.1.1. Administration Site Reactions**

Administration site reactions will be defined based on:

- MedDRA High Level Group Term (HLGT): Administration Site Reactions

Summaries will be presented by high level term (HLT), preferred term, and previous double-blind treatment group. Patients will further be assessed on a 4-point Likert scale (none, mild, moderate, severe) for several domains of localized injection site tolerability including pain, tenderness, erythema, warmth, and swelling. The number and percentage of patients reported for each of the levels will be summarized descriptively for each domain by visit.

#### **8.3.1.2. Anaphylaxis and Hypersensitivity**

Anaphylaxis and hypersensitivity events will be defined based on:

- MedDRA SMQ: Anaphylactic Reaction
- MedDRA SMQ: Hypersensitivity

Summaries will be presented separately for both the broad (broad+narrow) and narrow preferred terms by previous double-blind treatment group.

Adverse events suspected by the investigator to be anaphylaxis events will be summarized by preferred term and double-blind treatment group. Supplemental information related to the relative timing, clinical manifestation, and treatment of these suspected events will be collected in a dedicated CRF and reported in the patient listings.

#### **8.3.1.3. Malignancies**

Malignancies will be defined based on:

- MedDRA SMQ: Malignant Tumors

Summaries will be presented by preferred term and previous double-blind treatment group.

#### **8.3.1.4. Helminth infections**

Helminth infections will be defined based on:

- MedDRA HLGT: Helminthic Disorders

Summaries will be presented by HLT, preferred term, and previous double-blind treatment group.

### 8.3.1.5. Muscle Disorders

Muscle disorders will be defined based on:

- MedDRA HLGT: Muscle Disorder
- MedDRA PT: Blood Creatine Phosphokinase Increased

Summaries will be presented by HLT, preferred term, and previous double-blind treatment group.

### 8.3.1.6. Opportunistic Infections

Opportunistic infections will be defined based on the following list of terms, derived from the preferred term (PT) or low level term (LLT) summarized in [Table 4](#). Food and Drug Administration (FDA) terms provided are from the Panel on Opportunistic Infections in HIV-Infected Adults and Adolescents.

Summaries will be presented by preferred term and previous double-blind treatment group.

**Table 4: List of Terms for Opportunistic Infections**

Term	Code	Level	List from Panel on Opportunistic Infections in HIV-Infected Adults and Adolescents	If LLT- under which PT
Acinetobacter infection	10051894	PT	Acinetobacter infection	
Acinetobacter bacteraemia	10064965	PT	Acinetobacter infection	
Aspergillus infections	10003486	HLT	Aspergillosis	
Blastomycosis	10005098	PT	Blastomycosis, extrapulmonary	
Epididymitis blastomycetes	10015001	PT	Blastomycosis, extrapulmonary	
Osteomyelitis blastomycetes	10031255	PT	Blastomycosis, extrapulmonary	
Burkitt's lymphomas	10006596	HLT	Burkitt's lymphoma	
Oesophageal candidiasis	10030154	PT	Candidiasis of esophagus	
Cerebral toxoplasmosis	10057854	PT	Toxoplasmosis of brain	
Meningitis toxoplasmal	10048848	PT	Toxoplasmosis of brain	
Cervix carcinoma	10008342	PT	Cervical cancer invasive	
Cervix carcinoma stage II	10008346	PT	Cervical cancer invasive	
Cervix carcinoma stage III	10008347	PT	Cervical cancer invasive	

